8. OUTPUT PRESENTATIONS

The templates provided with this SAP describe the presentations for this study and the format and content of the summary tables, figures, and listings are to be provided by IQVIA Biostatistics.

All visit assessments will be presented according to the nominal visit name.

9. DISPOSITION AND WITHDRAWALS

All patients who provide informed consent will be accounted.

Data collected in Early Termination (ET) and End of Study (EOS) pages in the electronic Case Report Form (eCRF) will be used to present disposition and withdrawal results. Frequency table will be provided for:

number of patients in the All Patients Screened Set (provided informed consent and demographic details available)

number of patients eligible at screening

number of patients eligible at Day 1

number of screen failures

number of patients in the Randomized Analysis Set

number of patients administered the treatment

number of patients in the Full Analysis Set

number of patients in the Safety Analysis Set

number of patients in the Pharmacokinetic Analysis Set

number of patients in the Pharmacodynamic Analysis Set

number of patients who discontinued the study

primary reason for discontinuation

number of patients who completed the study

A listing will be presented with the following details.

screening date

Document: \\ieedc-nas01a\biosdata\AnaptysBio\ANB020\CYA74393\Biostatistics\Documentation\SAP\Final2018-02-07
Author: [REDACTED] Version Number: Final 1.0
Version Date: 07Feb2018

STATISTICAL ANALYSIS PLAN

AnaptysBio Inc
PROTOCOL ANB020-003
Page 20 of 36

assigned treatment

screen failure (Yes/No)?

completed study (Yes/No)?

If not completed the study, then reason for discontinuation

A separate listing will be presented of eligibility criteria deviations for which the all patient screened population will used.

10. DEMOGRAPHIC AND OTHER BASELINE CHARACTERISTICS

Demographic data and other baseline characteristics will be presented for the Randomized Analysis Set. No statistical testing will be carried out for demographic or other baseline characteristics.

Summary statistics will be provided for:

Age (years) - calculated relative to date of consent

Weight (kg)

Height (cm)

BMI (kg/m²)

Frequency tables will be provided for:

Gender

Ethnicity

Race

A listing for patient demographic data and other baseline characteristics will be presented.

10.1. DERIVATIONS

BMI (kg/ m²) = weight (kg)/ height (m)²

11. PROTOCOL DEVIATIONS

All protocol deviations observed during study conduct will be captured in Clinical Trial Management System (CTMS).

Document: \\ieedc-nas01a\biosdata\AnaptysBio\ANB020\CYA74393\Biostatistics\Documentation\SAP\Final2018-02-07
Author: [REDACTED] Version Number: Final 1.0
Version Date: 07Feb2018

STATISTICAL ANALYSIS PLAN

AnaptysBio Inc
PROTOCOL ANB020-003
Page 21 of 36

The Investigator and Sponsor will review the protocol violation records from CTMS and provide confirmation on the categorization of violations as major or other.

Major protocol deviations or events include changes to the procedures that may impact the quality of the data or any circumstances that can alter the evaluation of the PK data. Examples include, but may not be limited to, sample processing errors that lead to inaccurate bioanalytical results, incomplete dose administered, incomplete PK profile collected, use of disallowed concomitant medication thought to affect PK. In the case of a major protocol deviation or event, affected PK data collected will be excluded from the summaries and statistical analyses, but will still be reported in the study result listings.

A frequency table for major protocol violations will be provided for Randomized Analysis Set. Major protocol deviations or events that impact the quality of the PK and/or PD data will be listed only.

A list of major protocol deviations that involve eligibility criteria or could significantly affect study assessments will be provided. The incidence of each protocol violation will be listed.

12. SURGICAL AND MEDICAL HISTORY

Frequency tables will be provided for medical history findings summarized by body system for the Randomized Analysis Set. Version 19.1 of Medical Dictionary for Regulatory Activities (MedDRA) will be used.

AEs due to BPCFC at screening visit will be captured as medical history.

A listing of medical history diagnoses with all details will be presented.

13. CONCOMITANT ILLNESSES

Not applicable.

14. CONCOMITANT MEDICATIONS

A frequency table will be provided for concomitant medications and will be summarized by Anatomic, therapeutic and chemical classification (ATC) Level 1 and 3 for Safety Analysis Set. Concomitant medication will be coded using WHO drug dictionary Version Dec 2016.

See [Appendix 1](#) for handling of partial dates for medications. If it is not possible to define a medication as prior, concomitant, or post treatment, the medication will be classified by the worst case; i.e.,

Document: \\ieedc-nas01a\biosdata\AnaptysBio\ANB020\CYA74393\Biostatistics\Documentation\SAP\Final2018-02-07
Author: [REDACTED] Version Number: Final 1.0
Version Date: 07Feb2018

STATISTICAL ANALYSIS PLAN

AnaptysBio Inc
PROTOCOL ANB020-003
Page 22 of 36

concomitant.

'Prior' medications are medications which started and stopped prior to the first dose of study medication.

'Concomitant' medications are medications which:

- o started prior to, on or after the first dose of study medication,
- o AND ended on or after the date of first dose of study medication or were ongoing at the end of the study.

A listing for medication with all details will be presented and safety analysis set will be used for the same.

15. STUDY MEDICATION EXPOSURE

A listing of exposure to Investigational Product will be presented, with details of start and end time of infusion, interruptions, and total volume administered. IP Administration data will be used to generate the listing.

16. STUDY MEDICATION COMPLIANCE

Overall compliance is expected as the study medication is being administered at the clinic, however no summary will be provided for compliance.

17. EFFICACY OUTCOMES

17.1. PRIMARY EFFICACY

17.1.1. PRIMARY EFFICACY ENDPOINT

The difference in total cumulative tolerated peanut dose during BPCFC between post-treatment and baseline, following treatment with ANB020 or placebo on Day 14.

17.1.2. ANALYSIS OF PRIMARY EFFICACY ENDPOINT

The null hypothesis for the primary efficacy analysis is:

H0: There is no difference in change from baseline on day 14 for total cumulative tolerated peanut dose during BPCFC between ANB020 and placebo.

Document: \\ieedc-nas01a\biosdata\AnaptysBio\ANB020\CYA74393\Biostatistics\Documentation\SAP\Final2018-02-07
Author: [REDACTED] Version Number: Final 1.0
Version Date: 07Feb2018

STATISTICAL ANALYSIS PLAN

AnaptysBio Inc
PROTOCOL ANB020-003
Page 23 of 36

Vs the alternative:

H1: There is a difference in change from baseline on day 14 for total cumulative tolerated peanut dose during BPCFC between ANB020 and placebo

The primary efficacy analysis will be carried out for the FAS population.

The actual and change from baseline values of primary efficacy endpoints will be summarized using appropriate descriptive statistics by treatment at all time points where assessment is done. Change from baseline will be evaluated where possible.

Regarding the primary efficacy endpoint, change from baseline on day 14 of tolerated dose will be compared between ANB020 and placebo using an ANCOVA with treatment as fixed effect and baseline results as a covariate.

The following statistics will be presented:

- o Treatment difference
- o Standard error of treatment difference
- o 95% CI
- o p-value

The treatment difference and 95% CI will also be presented graphically.

Patient-wise data listings will be provided.

17.2. SECONDARY EFFICACY

17.2.1. SECONDARY EFFICACY ENDPOINT

Clinical scores of OFC Symptom Scoring Assessment Tool on Day 14

17.2.2. SECONDARY PHARMACOKINETIC ENDPOINT

Maximum observed concentration (C_{max})

Time to maximum observed concentration (t_{max})

17.2.3. ANALYSIS OF SECONDARY EFFICACY ENDPOINT

The analysis of the secondary efficacy endpoint will be carried out in the similar way as of primary efficacy endpoint for FAS population.

Document: \\ieedc-nas01a\biosdata\AnaptysBio\ANB020\CYA74393\Biostatistics\Documentation\SAP\Final2018-02-07
Author: [REDACTED] Version Number: Final 1.0
Version Date: 07Feb2018

Template No: CS_TP_BS016 Revision 4
Effective Date: 01Apr2016

Reference: CS_WI_BS005

STATISTICAL ANALYSIS PLAN

AnaptysBio Inc
PROTOCOL ANB020-003
Page 24 of 36

For analysis of secondary PK endpoints, refer to [Section 19](#) for details.

17.3. EXPLORATORY EFFICACY

17.3.1. EXPLORATORY EFFICACY ENDPOINTS

The difference in total cumulative tolerated peanut dose during BPCFC between post-treatment and baseline, following treatment with ANB020 or placebo on Day 45

Clinical scores of OFC Symptom Scoring Assessment Tool on Day 45

17.3.2. EXPLORATORY PHARMACODYNAMICS ENDPOINTS

Serum cytokines will be evaluated including, but not be limited to, IL-4, IL-5, IL-9, IL-13, IL-33, and sST2

Differential white blood cell counts (WBC) in the whole blood will be measured to monitor circulating leukocyte populations

For the ex vivo peanut antigen challenge, the whole blood peanut response assay will measure the cytokine levels released from pathogenic T cells

17.3.3. ANALYSIS OF EXPLORATORY EFFICACY ENDPOINTS

The Full Analysis Set will be used for the efficacy analysis.

The actual and change from baseline values of all the exploratory endpoints will be summarized using appropriate descriptive statistics by treatment at all time points where assessment is done. Change from baseline will be evaluated where possible.

Change from baseline on day 45 for tolerated dose and OFC symptom scores will be compared between ANB020 and placebo using a mixed model for repeated measures with treatment, visit, and treatment by visit interaction as fixed effect, and baseline and baseline by visit terms as covariates. The data collected at baseline, day 14, and day 45 will be used in the model.

The following statistics will be presented:

- o Treatment differences
- o Standard error of treatment difference
- o 95% CI
- o p-value

Document: \\ieedc-nas01a\biosdata\AnaptysBio\ANB020\CYA74393\Biostatistics\Documentation\SAP\Final2018-02-07
Author: [REDACTED] Version Number: Final 1.0
Version Date: 07Feb2018

Template No: CS_TP_BS016 Revision 4
Effective Date: 01Apr2016

Reference: CS_WI_BS005

STATISTICAL ANALYSIS PLAN

AnaptysBio Inc
PROTOCOL ANB020-003
Page 25 of 36

An appropriate covariance matrix (e.g., unstructured [UN]) will be used in the model.

The treatment difference and 95% CI will also be presented graphically.

Patient-wise data listings will be provided.

For analysis of exploratory PD endpoints, refer [Section 20](#) for details.

18. SAFETY OUTCOMES

Safety outcomes will be based on the Safety Analysis Set defined in [Section 6](#).

There will be no statistical comparisons between the treatment groups for safety data.

18.1. ADVERSE EVENTS

Adverse Events (AEs) will be coded using MedDRA Version 19.1.

Treatment emergent adverse events (TEAEs) are defined as AEs that started or worsened in severity on or after the date and time of the IP infusion or if the event represents an exacerbation of a condition observed pre-treatment. This excludes AEs due to BPCFC. AEs due to BPCFC during screening visit will be captured in medical history events.

Non treatment emergent adverse event (Non-TEAE) will be defined as any AE that started after the informed consent form has been signed and before the first dose of study medication and did not qualify for TEAE in terms of severity.

Adverse events with missing start dates will be considered treatment-emergent. AEs with missing stop dates or with stop dates after the end of the study date will be considered to have been ongoing at the end of the study.

The relationship to investigational product will be presented as "Related" versus "Not Related". Here the relationship categories "Unrelated" and "Unlikely" collected in the eCRF will be mapped to "Not Related", while the categories "Possible", "Probable" and "Unknown" will be mapped to "Related".

For each treatment, numbers of events, patients experiencing adverse events and percentage will be tabulated. The following summary tables will be provided by system organ class and preferred term for each treatment group:

- o number of patients with at least one TEAE
- o number of patients with at least one serious TEAE

Document: \\ieedc-nas01a\biosdata\AnaptysBio\ANB020\CYA74393\Biostatistics\Documentation\SAP\Final2018-02-07
Author: [REDACTED] Version Number: Final 1.0
Version Date: 07Feb2018

STATISTICAL ANALYSIS PLAN

AnaptysBio Inc
PROTOCOL ANB020-003
Page 26 of 36

- o number of patients with at least one TEAE by severity
- o number of patients with at least one TEAE by relationship to IP
- o number of patients with at least one TEAE leading to discontinuation from the study
- o number of patients with at least one TEAE leading to interruption of IP
- o number of patients with at least one TEAE leading to death
- o number of patients with non-TEAE
- o number of patients with AEs due BPCFC

When calculating the number of patients who experience an AE, an event that occurred one or more times on treatment will contribute one observation to the numerator and denominator for all safety patients exposed to ANB020 or placebo for the respective treatment, i.e., the event will be counted only once per SOC and per PT with highest severity and worst relationship with IP.

Listings will be provided for TEAEs, Serious TEAEs, TEAEs leading to discontinuation from study or of IP, and TEAEs leading to deaths for safety analysis set.

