18.2. DEATHS

The number of patients with at least one TEAE leading to death will be summarized and listed as described above.

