OFC Symptom Score	xxxx xxx (xxxx xxx)	xxxx xxx (xxxx xxx)	xxx xx (xxx xxx)	(xxx xx, xxx xx)

Note:

- P-value is obtained using MMRM model with treatment, visit, treatment*visit as fixed effects and baseline and baseline*visit as covariates

Programming Note: Refer SAP for Model

Table Shells

AnaptysBio Inc.
PROTOCOL ANB020-003
Page 23 of 42

Table 14 3 1 1
Overview of Adverse Events – Safety Analysis Set

Characteristic	ANB020 (N=XX) n (%)	Placebo (N=XX) n (%)	Total (N=XX) n (%)
Overall number of TEAEs	xx	xx	xx
Overall number of Non-TEAEs	xx	xx	xx
Overall number of AE due to BPCFC	xx	xx	xx
Number of Patients with at least one TEAE	xx (xx x)	xx (xx x)	xx (xx x)
Serious TEAE	xx (xx x)	xx (xx x)	xx (xx x)
Severe TEAE	xx (xx x)	xx (xx x)	xx (xx x)
Related TEAE	xx (xx x)	xx (xx x)	xx (xx x)
Non-TEAE	xx (xx x)	xx (xx x)	xx (xx x)
AE due to BPCFC	xx (xx x)	xx (xx x)	xx (xx x)
Patients with TEAE by Severity			
Mild	xx (xx x)	xx (xx x)	xx (xx x)
Moderate	xx (xx x)	xx (xx x)	xx (xx x)
Severe	xx (xx x)	xx (xx x)	xx (xx x)
Patients with TEAE by Final Outcome			
Recovered	xx (xx x)	xx (xx x)	xx (xx x)
Recovering	xx (xx x)	xx (xx x)	xx (xx x)
Not Recovered	xx (xx x)	xx (xx x)	xx (xx x)
Recovered with Sequelae	xx (xx x)	xx (xx x)	xx (xx x)
Fatal	xx (xx x)	xx (xx x)	xx (xx x)
Lost to Follow-Up	xx (xx x)	xx (xx x)	xx (xx x)
Action Taken with the Study Drug for Patients with TEAE			
Drug Permanently Discontinued	xx (xx x)	xx (xx x)	xx (xx x)
Dose Reduced	xx (xx x)	xx (xx x)	xx (xx x)
Dose Interrupted	xx (xx x)	xx (xx x)	xx (xx x)
Dose Not Changed	xx (xx x)	xx (xx x)	xx (xx x)
None	xx (xx x)	xx (xx x)	xx (xx x)
Patients with TEAE with Relationship to Study Drug			
Unrelated	xx (xx x)	xx (xx x)	xx (xx x)
Unlikely	xx (xx x)	xx (xx x)	xx (xx x)

Document: \\ieedc-nas01a\biosdata\AnaptysBio\ANB020\CYA74393\Biostatistics\Documentation\SAP\Draft\2018-02-07
Author: [REDACTED]

Version Number: Draft 3.0
Version Date: 07Feb2018

Table Shells

AnaptysBio Inc.
PROTOCOL ANB020-003
Page 24 of 42

Table 14 3 1 1
Overview of Adverse Events – Safety Analysis Set

Characteristic	ANB020 (N=XX) n (%)	Placebo (N=XX) n (%)	Total (N=XX) n (%)
Possible	xx (xx x)	xx (xx x)	xx (xx x)
Probable	xx (xx x)	xx (xx x)	xx (xx x)
Unknown	xx (xx x)	xx (xx x)	xx (xx x)
Patients with TEAE with Seriousness Criteria			
Death	xx (xx x)	xx (xx x)	xx (xx x)
Life-Threatening	xx (xx x)	xx (xx x)	xx (xx x)
Inpatient Hospitalization or Prolongation of Existing Hospitalization	xx (xx x)	xx (xx x)	xx (xx x)

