Persistent or Significant Disability/ Incapacity	xx (xx x)	xx (xx x)	xx (xx x)
Congenital Abnormality/ Birth Defect	xx (xx x)	xx (xx x)	xx (xx x)
Other Medically Significant Events	xx (xx x)	xx (xx x)	xx (xx x)
Patients who Discontinued from the Study Due to TEAE			
	xx (xx x)	xx (xx x)	xx (xx x)

Source: Listing 16 3 1 1, 16 3 2 1, 16 3 3 1, 16 3 4 1

Note:

- N is the number of patients within each treatment group under Safety Analysis Set
- Adverse Event terms are coded using latest version of MedDRA
- Patients experiencing multiple events are counted only once within the treatment group
- Percentages are based on number of patients within each treatment group under Safety Analysis Set (N)
- AE- Adverse Event, TEAE- Treatment Emergent Adverse Events

Programming Note (not part of table): For count of TEAEs, use the coded term (preferred term)

Document: \\ieedc-nas01a\biosdata\AnaptysBio\ANB020\CYA74393\Biostatistics\Documentation\SAP\Draft\2018-02-07
Author: [REDACTED]

Version Number: Draft 3.0
Version Date: 07Feb2018

Table 14 3 1 2
TEAE by System Organ Class and Preferred Term – Safety Analysis Set

System Organ Class Preferred Term	ANB020 (N=XX)	Placebo (N=XX)	Total (N=XX)
Number of Patients with at least one TEAE	xx (xx x)	xx (xx x)	xx (xx x)
System Organ Class 1	xx (xx x)	xx (xx x)	xx (xx x)
Preferred Term 1	xx (xx x)	xx (xx x)	xx (xx x)
Preferred Term 2	xx (xx x)	xx (xx x)	xx (xx x)
System Organ Class 2	xx (xx x)	xx (xx x)	xx (xx x)
Preferred Term 1	xx (xx x)	xx (xx x)	xx (xx x)

Source: Listing 16 3 1 1, 16 3 2 1, 16 3 3 1, 16 3 4 1

Note:

- N is the number of patients within each treatment group under Safety Analysis Set
- Adverse Event terms are coded using System Organ Class and Preferred term using latest version of MedDRA
- Patients experiencing multiple events within the same SOC or PT are counted only once under those categories
- Percentages are based on number of patients within each treatment group under Safety Analysis Set (N)

Programming Note (not part of table):

- Table will be sorted in decreasing frequency of system organ class and preferred term of total column. Include "Uncoded" if events are not coded
A subject can have one or more preferred terms reported under a given system organ class
- Similar tables will be generated for Safety Analysis Set as follows:

Table 14 3 1 2 1 TEAEs by Preferred Term – Safety Analysis Set

Table 14 3 1 3 Serious TEAEs by System Organ Class and Preferred Term – Safety Analysis Set

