Table 14 3 1 4 TEAEs Leading to Discontinuation from the Study by System Organ Class and Preferred Term – Safety Analysis Set

Table 14 3 1 5 TEAEs Leading to Interruption of Study Drug by System Organ Class and Preferred Term – Safety Analysis Set

Table 14 3 1 6 TEAEs Leading to Death by System Organ Class and Preferred Term – Safety Analysis Set

Table 14 3 1 7 Non TEAEs by System Organ Class and Preferred Term – Safety Analysis Set

Table 14 3 1 8 Adverse Events due to BPCFC by System Organ Class and Preferred Term – Safety Analysis Set

Table 14 3 2 1
TEAEs by Severity, System Organ Class and Preferred Term – Safety Analysis Set

System Organ Class Preferred Term	ANB020 (N=XX)			Placebo (N=XX)		
	Mild	Moderate	Severe	Mild	Moderate	Severe
Number of Patients with at least one TEAE by Severity	xx (xx x)	xx (xx x)	xx (xx x)	xx (xx x)	xx (xx x)	xx (xx x)
System Organ Class 1	xx (xx x)	xx (xx x)	xx (xx x)	xx (xx x)	xx (xx x)	xx (xx x)
Preferred Term 1	xx (xx x)	xx (xx x)	xx (xx x)	xx (xx x)	xx (xx x)	xx (xx x)
Preferred Term 2	xx (xx x)	xx (xx x)	xx (xx x)	xx (xx x)	xx (xx x)	xx (xx x)
System Organ Class 2	xx (xx x)	xx (xx x)	xx (xx x)	xx (xx x)	xx (xx x)	xx (xx x)
Preferred Term 1	xx (xx x)	xx (xx x)	xx (xx x)	xx (xx x)	xx (xx x)	xx (xx x)

Source: Listing 16 3 1 1, 16 3 2 1, 16 3 3 1, 16 3 4 1

Note:

- N is the number of patients within each treatment group under Safety Analysis Set
- Adverse Event terms are coded using System Organ Class and Preferred term using latest version of MedDRA
- Patients experiencing multiple events within the same SOC or preferred term are counted only once under those categories
- Percentages are based on number of patients within each treatment group under Safety Analysis Set (N)
- Patients experiencing the same event with different severity level are counted under the most severe occurrence

Programming Note (not part of table):

- Table will be sorted in decreasing frequency of system organ class and preferred term of total column. Include "Uncoded" if events are not coded
- A subject can have one or more preferred terms reported under a given system organ class

Table 14 3 2 1
TEAEs by Severity, System Organ Class and Preferred Term – Safety Analysis Set

System Organ Class Preferred Term	Mild	Total (N=XX)	
		Moderate	Severe
Number of Patients with at least one TEAE by Severity	xx (xx x)	xx (xx x)	xx (xx x)
System Organ Class 1	xx (xx x)	xx (xx x)	xx (xx x)
Preferred Term 1	xx (xx x)	xx (xx x)	xx (xx x)

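### By-arm tables of serious, severe, fatal and discontinuation AEs leave out post-dose food-challenge reactions, an undeclared departure from Protocol 9.4.1

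*SAP*

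**What the plan says.** SAP 18.1 defines a TEAE as an AE that begins or worsens from the time of the infusion, and adds "This excludes AEs due to BPCFC". Section 12 says "AEs due to BPCFC at screening visit will be captured as medical history", and 18.1 repeats this.

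The 18.1 summaries of seriousness, severity, relationship to IP, discontinuation from the study and death are all worded as counts of patients with a TEAE. For listings it says "Listings will be provided for TEAEs, Serious TEAEs, TEAEs leading to discontinuation from study or of IP, and TEAEs leading to deaths". Section 18.2 says "The number of patients with at least one TEAE leading to death will be summarized and listed as described above".

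For challenge reactions, the shells provide:
- in overview Table 14.3.1.1, a row "Overall number of AE due to BPCFC" and a row for patients with such an AE;
- Table 14.3.1.8, "Adverse Events due to BPCFC by System Organ Class and Preferred Term";
- Listing 16.2.7.5, by patient.

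The attribute rows of Table 14.3.1.1 are TEAE rows, for example "Patients with TEAE with Seriousness Criteria".

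Protocol 9.4.1 plans by-treatment summaries of AEs, AEs leading to death, SAEs and AEs leading to discontinuation, and further summaries by relatedness and severity. It makes no exception for the food challenge. Protocol 9.0 says changes to the analysis methods will be documented in the SAP. SAP 3.3 reports none.

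**The concern.** Safety and tolerability is a primary objective, and the trial deliberately exposes allergic patients to peanut after dosing. The most foreseeable serious event after dosing is a reaction to that challenge. If it is removed from the TEAE category and every table of serious and fatal events is built on TEAEs, those tables can show no event in either arm when one has occurred. A reader would normally take the SAE and death tables as complete and would have no cue in them to look elsewhere.

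**Working it through.** No figure in the plan needs reproducing, so the check sets the passages side by side.

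**Step 1: what the exclusion removes.** The sentence in 18.1 is not limited to any visit. A screening reaction precedes the infusion and is routed to medical history. The sentence therefore acts on challenges after dosing: Day 14/15, Day 45/46, and any challenge at an early termination visit between Day 35 and Day 45 (Protocol 6.2.6). Such a reaction is not a non-TEAE either, because 18.1 reserves that class for events before the first dose. It falls in a third class, AEs due to the challenge.

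**Step 2: which by-arm AE table gives each attribute.**

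| Attribute | Planned in Protocol 9.4.1 | By-arm SAP table | What it counts | By-arm equivalent for challenge AEs |
|---|---|---|---|---|
| Serious | Yes | 14.3.1.3 | TEAEs | None |
| Severity | Yes | 14.3.2.1 | TEAEs | None |
| Relationship to IP | Yes | 14.3.3.1 | TEAEs | None |
| Study discontinuation | Yes | 14.3.1.4 | TEAEs | None |
| Death | Yes | 14.3.1.6 and section 18.2 | TEAEs | None |

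The matching rows of Table 14.3.1.1 are also TEAE rows.

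**Step 3: trace one event.** Suppose a patient is hospitalised after the Day 14 peanut challenge and the event is attributed to the challenge.
- Table 14.3.1.1: one more challenge AE and one more patient with a challenge AE; nothing in the serious or severe TEAE rows.
- Table 14.3.1.8: one patient under the system organ class and preferred term.
- Table 14.3.1.3 and Listing 16.2.7.3 (serious TEAEs): nothing.
- Listing 16.2.7.5: a row with treatment, severity, outcome, relationship, seriousness criterion and study discontinuation.

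If the event were fatal, Table 14.3.1.6, section 18.2 and Listing 16.2.7.4 would also show nothing. Disposition Table 14.1.1.1 has Death and Adverse Event among its reasons for discontinuation, with no TEAE limit, so the case could appear there by arm, without its cause.

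**Step 4: is it a version difference?** The SAP cites protocol Amendment 3. The summaries of changes for Amendments 4 and 5 list nothing for 9.4.1, so a later amendment does not explain the mismatch.

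**Step 5: denominators.** The Safety Analysis Set includes everyone who received any part of the infusion, including patients who left before Day 14 and were replaced (Protocol 4.3.5). The Day 45 challenge is not required after an objective Day 14/15 reaction (Protocol 6.2.5). The number challenged can therefore be smaller than the Safety Set N, and no AE shell displays it.

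**The case against.** The strongest reply is that the separation is sensible and the events are reported. Challenge reactions are provoked and expected, and mixing them with other AEs would obscure drug tolerability. They have their own by-arm counts, a by-arm table by preferred term, and a listing with the attributes at issue. With about 20 patients, a reader can count serious cases from one listing. Symptom grades from the challenge are also summarised by arm. The SAP states the exclusion openly in 18.1, and Protocol 9.4.1 is silent on challenge reactions rather than requiring their inclusion.

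Much of this stands. The separate category should stay, and four stronger readings are not supported:
- A reader might infer that challenge reactions disappear from the report. They do not; Step 3 shows where they appear.
- A reader might infer that a death would be invisible by arm. Table 14.1.1.1 may show it, unattributed.
- A reader might infer that nearly all AE output is distorted. Summaries of IP interruption and action taken with study drug are unaffected, because the only dose is a one-hour infusion on Day 1.
- A reader might infer that the SAP contradicts itself, because the known-date rows of Appendix 1 class any AE starting on or after dosing as a TEAE. That appendix covers partial dates and is most naturally read as subordinate to 18.1. This is a matter of alignment.

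What the reply does not answer is that a listing is not the by-treatment summary Protocol 9.4.1 plans. The symptom scores do not fill the gap: they are analysed in the Full Analysis Set, which requires post-baseline challenge and score results, and they record neither AE seriousness nor fatal outcome. Stating the exclusion in 18.1 also does not make the statement in 3.3 correct.

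**Conclusion.** The point holds as a reporting defect. For five attributes (seriousness, severity, relationship, study discontinuation, death) the by-arm AE tables exclude post-dose challenge reactions and offer no equivalent for them. The by-arm SAE and death tables could therefore read zero despite a serious or fatal reaction. Protocol 9.4.1 has no such exclusion, and SAP 3.3 is wrong to say nothing changed.

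The defect is one of aggregation and labelling; no data are missing. The conclusion assumes that the 18.1 exclusion is programmed as written and that such a reaction is recorded as due to the challenge. The documents give no expected frequency of serious challenge reactions, so nothing is claimed about how likely a misleading zero is. They also give no fixed denominator from which a rate could be quoted: enrolment is approximate, replacements can enlarge the Safety Set, and the number challenged on Day 45 is unknown in advance.

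**What to change.** Keep challenge reactions as their own category and make these changes:

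1. Add by-arm rows or one table of post-dose challenge AEs by severity, seriousness, study discontinuation and fatal outcome, on the Safety Analysis Set, with the number of patients challenged displayed.
2. Present post-dose SAEs, and AEs leading to study discontinuation, with and without challenge-attributed events.
3. Have section 18.2 count all deaths, flagging any attributed to the challenge.
4. Declare the exclusion in SAP 3.3 as a departure from Protocol 9.4.1.
5. State in Appendix 1 that the 18.1 exclusion applies before the date algorithm.

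The cost is SAP wording and a little more table work. No new data are needed, since Listing 16.2.7.5 already carries the required fields. SAE and discontinuation counts may be higher in the all-events version. Any Day 45 figures should be labelled descriptive, because patients challenged then may be a selected group.
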